5. Study Design/procedures:

- a. Study design, including the sequence and timing of study procedures (distinguish research procedures from those that are part of routine care).

Study Schema:

Notes:

^aInclusion criteria: MSM/TGW; IDU; Known STI or being screened for STI; High prevalence network; Living with HIV with unsuppressed HIV VL in past 6 months; Not taking daily PrEP.

^bInclusion criteria: MSM/TGW; IDU; Known STI or being screened for STI; High prevalence network; Living with HIV.

^cMedical exam – abstract from clinical notes if appropriate

^dOutcomes

Primary Outcome: Proportion linked either to PrEP or ART

Secondary Outcomes:

- 1) HIV: HIV case identification, time to linkage to PrEP or ART; proportion of positives started on ART, proportion virally suppressed at 12 weeks
- 2) Syphilis: linkage to syphilis treatment
- 3) HIV 'knowledge' – behavioral change (awareness/risk behavior change) since the time of diagnosis

Patients attending clinical services will undergo their usual clinical procedures prior to joining the study; all SOC testing will be performed as usual. Potential study participants will be asked if they are interested in taking part in the study. Those who express an interest in the study will be introduced to a member of the research team to discuss the study, assess eligibility and provide written informed consent before any study procedures take place. Those who do not agree to participate will continue with their routine clinical care.

Some potential participants might be at high risk of poor sexual health outcomes, but may not meet inclusion criteria for the randomized group because they are unable or unwilling to commit to the follow-up portion of the study or are taking daily ART or PrEP. In order to maximize equity of access to research opportunities for those described above, a non-randomized group will be made available. Those in the non-randomized group will be offered rapid and laboratory-based HIV and syphilis diagnostics, will be appropriately linked to care, and will have a telephone and/or an email follow-up interview at 4 weeks after their enrollment visit.

Inclusion:

- Aged 18 years or older
- At high risk for HIV and STIs (e.g., patients who receive STI, HIV and/or HCV testing, or treatment for STI)
- Willing to undergo phlebotomy and collection of oral fluid samples
- Willing to complete a questionnaire

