To maximize recruitment efforts and facilitate access to research to the broadest possible community, we will invite members of the public to consider joining the study. We will target key populations, including PrEP users, MSM, and transgender people through outreach to trusted community-based organizations (CBOs). Information will be made available through social media and more traditional methods, such as posters and flyers. Individuals who contact the study team expressing an interest in the study will be invited to the ICTR CRUs.

Prior to study enrollment, the study team will confirm that people who are recruited via non-clinic venues have a medical provider who can be contacted with the results of positive study laboratory results. If a participant does not have a provider, the study team will confirm that they are willing to be referred to an appropriate provider for care and treatment.

Venue for follow up visits and sample collection

Study participants who are recruited from the non-clinical sites described above will be asked to come to the ICTR-CRUs. Similarly, for those with discordant HIV results (recruited from any location) will attend the CRU, Bartlett Clinic, and BCHD for their follow up visits.

7. Drugs/ Substances/ Devices:

- a. The rationale for choosing the drug and dose or for choosing the device to be used.

In this study, we will be testing performance of point of care (POC) devices, Chembio DPP HIV-Syphilis and OraQuick Advance HIV test, for rapid detection of HIV and Syphilis antibodies. Participants in the intervention (POC) arm will also receive nucleic acid amplification test for HIV viral load quantification using Roche Cobas HIV-1 Realtime PCR test and/or Cepheid GeneXpert HIV-1 viral load test.

We acknowledge in-kind contribution (non-monetary support), as Roche Diagnostics and Cepheid have agreed to provide test kits (cartridges) for this study.

- b. Justification and safety information if FDA approved drugs will be administered for non-FDA approved indications or if doses or routes of administration or participant populations are changed.

NA

- c. Justification and safety information if non-FDA approved drugs without an IND will be administered.

NA

8. Study Statistics:

- a. Primary outcome variable.

Proportion of participants linked either to PrEP or ART

- b. Secondary outcome variables.

Syphilis: linkage to syphilis treatment and time to linkage

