HIV: time to linkage to either PrEP or ART; HIV case identification; proportion of persons with HIV started on ART; proportion of persons with HIV and on ART who are virally suppressed at 12 weeks.

HIV ‘knowledge’ – behavioral change (awareness/risk behavior change) since the time of diagnosis.

- c. Statistical plan including sample size justification and interim data analysis.

With a LTC rate of 30% for known positive ED patients who are not in care and a ballpark estimated LTC rate of 50% in STD patients, this translates into an aggregate LTC rate of 40% (assuming 50% patient enrollment in the ED and 50% in the STD clinics). For the randomized group, assuming that the aggregate LTC rate will increase from 40% to 55% after the intervention (POC VL testing), a total of 173 participants are required to enroll in each arm to have a power of 80% to detect the increase of LTC rate from 40% to 55% with a two-sided significant level of 0.05. Factoring in 15% non-response rate, we will need 204 participants in each arm, respectively.

For the non-randomized group, we will recruit up to 1100 participants for the purpose of testing the performance characteristics of rapid tests for HIV and syphilis against SOC laboratory tests, and to bank biospecimens for future evaluation of new POC assays.

We will first analyze descriptive data to determine the proportion of participants linked either to PrEP or ART and the time to linkage; the proportion HIV positive; the proportion with no prior syphilis history who needed treatment; the proportion in which the treponemal test had no added value; the proportion of patients who would still be in the ED/STD clinic at the time the test resulted (for PrEP or ART provision); the proportion of those testing HIV positive who were started on ART; the proportion of those testing positive and started on ART who were virally suppressed at 12 weeks; and the proportion of those with syphilis who are linked to syphilis treatment. This will

be followed by bivariate analysis to explore the potential association between the independent variable (POC HIV VL test) and other covariates with the outcome variable of interest. Then, we will perform multivariate regression to determine the association between having a POC HIV VL test and linkage to PrEP or ART, with adjustment of covariates and confounders.

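### Week-12 viral suppression is defined only among people on ART, a group the intervention itself may change, so a comparison by arm would not be a randomised one and could favour the wrong arm.

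*Combined protocol and SAP*

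**What the plan says.** Suppression is worded in three ways:

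- Section 8.b: "proportion of persons with HIV and on ART who are virally suppressed at 12 weeks".
- Section 8.c: "the proportion of those testing positive and started on ART who were virally suppressed at 12 weeks".
- Section 5, schema note d: "proportion of positives started on ART, proportion virally suppressed at 12 weeks", with no ART condition on the suppression part.

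ART start has a wider denominator: "proportion of persons with HIV started on ART" in 8.b and "the proportion of those testing HIV positive who were started on ART" in 8.c. The primary outcome (8.a) is "Proportion of participants linked either to PrEP or ART".

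On analysis, 8.c puts both proportions in a list that opens "We will first analyze descriptive data to determine the proportion of participants linked either to PrEP or ART and the time to linkage". That list is to "be followed by bivariate analysis to explore the potential association between the independent variable (POC HIV VL test) and other covariates with the outcome variable"; the text does not say which outcome is meant. The regression and Cox models that follow cover linkage to PrEP or ART only, and section 8.e does not mention suppression. The week-12 visit is for the randomised group only, so the outcome can only belong to that group.

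**The concern.** Whether a participant is on ART at week 12 is settled after randomisation, and linkage to ART is one of the two routes to the primary outcome. The trial is sized on POC testing raising linkage. If it does so among people with HIV, the suppression denominator in the POC arm holds people with no counterpart in the SOC denominator, and the two groups are no longer alike at baseline.

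The likely direction matters. People who reach treatment only because of an extra test may be harder to keep on it. If they are suppressed less often, they pull down the percentage among starters in the POC arm while adding to the number suppressed. The trial could then report worse suppression for a strategy that left more people suppressed.

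The wording also leaves the subset unclear. The randomised group admits people with HIV who lack a documented undetectable viral load in the last 6 months or who do not take medication every day. Some may therefore be on ART at entry. They are on ART but did not start it in the study, so 8.b and 8.c select different people.

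**Working it through.** **Inputs from the plan (8.c).** Linkage 40% v 55%, two-sided 0.05, 80% power, 173 per arm, 15% non-response, 204 per arm.

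**The plan's own figure.** With pooled variance and no continuity correction, n = [1.960 × √(2 × 0.475 × 0.525) + 0.842 × √(0.40 × 0.60 + 0.55 × 0.45)]² / 0.15² = 173 per arm, and 173 / 0.85 = 204. Both reproduce. The sample size is not at issue.

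**Assumptions.** The documents give no ART-start or suppression rates for people with HIV. I borrow 40% v 55% as ART start. I also assume that everyone who would start under SOC would start under POC testing, that this group is suppressed at the same rate *a* in both arms, that the extra 15% are suppressed at rate *x*, and that people not on ART are not suppressed.

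**Suppression among starters (planned denominator).** SOC = *a*. POC = (0.40*a* + 0.15*x*) / 0.55. Difference = (0.15 / 0.55)(*x* − *a*).

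**Suppression among all with HIV.** SOC = 0.40*a*. POC = 0.40*a* + 0.15*x*. Difference = 0.15*x*.

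| *a* / *x* | Starters, SOC v POC | Difference | All with HIV, SOC v POC | Difference |
|---|---|---|---|---|
| 80% / 50% (central) | 80.0% v 71.8% | −8.2 | 32.0% v 39.5% | +7.5 |
| 90% / 30% | 90.0% v 73.6% | −16.4 | 36.0% v 40.5% | +4.5 |
| 80% / 80% | 80.0% v 80.0% | 0.0 | 32.0% v 44.0% | +12.0 |
| 70% / 90% | 70.0% v 75.5% | +5.5 | 28.0% v 41.5% | +13.5 |

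With *a* from 70% to 90% and *x* from 30% to 90%, the starter difference runs from −16.4 to +5.5 points and the all-HIV difference from +4.5 to +13.5. The starter difference is negative exactly when *x* is below *a*. The all-HIV difference is positive by construction, because every extra starter can only add to the number suppressed.

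**ART start among those testing positive.** Let *b* be the true gain, *e* the relative increase in detected cases from POC testing, and *s* the ART-start rate in those extra cases. The POC rate is (0.40 + *b* + *e s*) / (1 + *e*), which falls to 40% when *e* = *b* / (0.40 − *s*).

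- For *b* = 15 points: *e* = 0.15 / 0.40 = 37.5% if none of the extra cases start, and 0.15 / 0.20 = 75% if 20% do.
- For *b* = 5 points: 12.5% and 25%.
- For *b* = 0, with 2% to 10% extra cases that never start: a shift of −0.8 to −3.6 points.

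**Precision.** The share of randomised participants with HIV is not stated. If it is 6% to 50% of 173 per arm (assumed), about 10 to 87 per arm have HIV. Power is then about 5% to 18% for 32.0% v 39.5% suppressed, and about 10% to 51% for 40% v 55% starting ART.

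**The case against.** The strongest reply is that the plan never commits to comparing suppression by arm. It is listed as descriptive, the models are for linkage, and the fix keeps the on-ART figure as descriptive anyway. This stands in part: a reader might infer that a biased arm test is prespecified, and the documents do not say so. But a named secondary outcome of a two-arm randomised group will be read by arm, the bivariate step leaves its outcome open, and no suppression measure with a denominator fixed at enrollment is offered.

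A reader might also infer that ART start has the same flaw. It does not. Its denominator is HIV status or a positive test. Known positives are eligible, and both arms get the SOC algorithm, the DPP and OraQuick, so only infections missed by all of these can differ by arm. Site figures suggest few new cases: 6% seroprevalence with 5% previously diagnosed at one emergency department, and 0.2% newly diagnosed in the other's testing programme. These describe site patients rather than the trial sample. One sentence in section 5 also promises a same-day viral load result without naming an arm; if it covers both arms, the difference shrinks further.

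It is fair, too, that the suppression rates are assumed and reversal is not certain. The range above includes positive values.

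Multiplying the two listed proportions would recover an overall figure under the 8.c wording. That is not a planned comparison, and it fails under 8.b, where being on ART is not the same as having started it. Finally, schema note d may be shorthand, but 8.b and 8.c still differ from each other.

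**Conclusion.** The point holds for viral suppression. Its denominator depends on ART status after randomisation, so a contrast by arm is not protected by randomisation. In the central illustration it shows −8.2 points where the measure over all with HIV shows +7.5. The reversal depends on extra starters being suppressed less often than the others. That is plausible, but the documents neither state nor rule it out, and the 40% v 55% is an aggregate linkage figure borrowed for people with HIV.

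For ART start, any bias is limited to infections missed by the tests common to both arms and is likely small. Reversing a true 15-point gain would take at least 37.5% more detected cases. The primary outcome and the sample size are unaffected. This is worth correcting before analysis, as a secondary outcome that is cheap to repair.

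**What to change.** 1. In 8.b and 8.c, define the by-arm outcome as the proportion suppressed at week 12 among all randomised participants with HIV at enrollment.
2. Set enrollment HIV status by one rule applied alike in both arms: prior diagnosis, SOC algorithm positive, or RNA detected on stored enrollment plasma. Use the same denominator for ART start.
3. Keep people with HIV who are not on ART in the denominator and use their week-12 RNA result, which section 5 already plans for everybody at that visit. Count a missing week-12 RNA as not suppressed, and add a sensitivity analysis, because attendance may differ between unblinded arms.
4. Keep suppression among those on ART as descriptive only, and reconcile 'on ART', 'started on ART' and schema note d.
5. Report the arm difference with a confidence interval; the group with HIV is probably too small for a useful test.

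The cost is wording, plus making sure that the batched qualitative RNA runs on frozen plasma (section 5.i) include SOC-arm enrollment samples. The reported suppression percentage will be lower than the on-ART figure.

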For participants in the randomized group, all eligible consented participants will be randomized to receive one of two testing arms using a computerized randomization system in the ratio of 1:1. Participants will be randomized to receive either POC HIV VL plus SOC testing or SOC testing only. Randomization will be performed by research staff after informed consent and verification of all eligibility criteria have been performed.

Early Withdrawals:

Participants who have provided consent and are enrolled, but who do not complete all study procedures at the time of enrollment, will be removed from the study and classified as early withdrawals. Participants may also be removed from the study early for failing to follow instructions, if continuation is deemed potentially harmful, or for any other reason at the discretion of the study principal investigator.

6. Study sites:

The following study sites are planned for the conduct of this study.

1. Johns Hopkins Medicine Emergency Department (JHMED)
2. The John G. Bartlett Specialty Practice (JGBSP), Johns Hopkins Hospital
3. The Baltimore City Health Department (BCHD) Health and Wellness Center, Sexual Health Clinics

These sites have been selected to provide optimal settings for patient interaction, and to provide access to patients at high risk of HIV infection.

Potential participants may be seen at any of the sites mentioned below or the Clinical Research Units (CRU) at the Institute for Clinical and Translational Research (ICTR).

Johns Hopkins Hospital Emergency Department (JHHED) is located in East Baltimore, Maryland. (Drs. [name] and [name]). The mission of JHHED is to provide a patient-centered care experience by world-class emergency health care providers. The JHH ED serves a predominantly socioeconomically-disadvantaged population in the metropolitan area with 60% from Baltimore City, one of the localities hardest hit by the HIV epidemic and 33% from Baltimore County. JHH adult ED patient population is comprised of 15% previous or current injection drug users, with a high prevalence of sexually transmitted infections (STIs) [21-23] and 6% HIV seroprevalence[24]. In FY 2022, the JHH ED had approximately 60,000 adult patient visits. Of these, approximately 65% of the patients were Black or African American and 5% had previously-diagnosed HIV

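### The 80% power is not justified for the PrEP-or-ART primary outcome: no PrEP-linkage rate, PrEP effect or expected HIV-positive share lies behind it.

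*Combined protocol and SAP*

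**What the plan says.** Section 8.a defines the primary outcome as "Proportion of participants linked either to PrEP or ART". Under the section 5 inclusion criteria, the randomised group takes two kinds of participant: people with HIV who lack a documented undetectable viral load in the last 6 months or do not take their medication daily, and people at risk who are not on daily PrEP. The study procedures in section 5 refer those who test negative for consideration of PrEP.

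The sample size in section 8.c starts from linkage to care (LTC). The ED input is introduced as "With a LTC rate of 30% for known positive ED patients who are not in care". The other input is "a ballpark estimated LTC rate of 50% in STD patients", with HIV status not stated. The two are averaged to 40%, "assuming 50% patient enrollment in the ED and 50% in the STD clinics". The 173 per arm is said "to have a power of 80% to detect the increase of LTC rate from 40% to 55" per cent, "with a two-sided significant level of 0.05". An allowance for 15% non-response gives 204 per arm.

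For the analysis, section 8.c plans descriptive proportions, then bivariate exploration, then a regression of linkage on the POC viral load test adjusted for covariates and confounders that it does not name.

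**The concern.** The outcome has two routes to success. A person with HIV succeeds through ART. A person who is and remains HIV-negative can succeed only through PrEP. The ED half of the control rate describes the first route alone, and nothing in the documents is identified as a rate for the second. Neither input rate nor the 15-point rise has a source in section 8.c, and the expected split between the two kinds of participant is not stated.

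The split may matter. Section 6 describes one ED "with a high prevalence of sexually transmitted infections (STIs) [21-23] and 6% HIV seroprevalence". That is the patient population of one site, not the enrolled mix, but no rule confines ED enrolment to known positives who are out of care.

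At stake is how a null result would be read. If the test raised ART linkage but did little for PrEP linkage, the pooled difference would be diluted, and a reader relying on the stated 80% could take the result as good evidence of no benefit. The planned descriptives include ART start among those testing positive, but no matching figure for PrEP linkage among those testing negative.

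**Working it through.** **Inputs from section 8.c.** Control rate 0.5 × 30% + 0.5 × 50% = 40%; intervention rate 55%; two-sided alpha 0.05; power 80%; non-response 15%. Allocation is 1:1 (section 5, Randomization).

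**Reproducing the plan.** With pooled variance under the null and p̄ = (0.40 + 0.55)/2 = 0.475:

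n = [1.960 × √(2 × 0.475 × 0.525) + 0.842 × √(0.40 × 0.60 + 0.55 × 0.45)]² / 0.15² = 172.8, so 173 per arm.

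173 / 0.85 = 203.5, so 204 per arm. Both figures match the plan.

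**Does the baseline rate matter by itself?** Power = Φ[(d − 1.960 × SE₀)/SE₁], where d is the difference, SE₀ = √(2p̄(1 − p̄)/n) and SE₁ = √((p₁(1 − p₁) + p₂(1 − p₂))/n). With n = 173 and d held at 15 points:

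| Control rate | 5% | 10% | 20% | 30% | 40% | 50% | 60% |
|---|---|---|---|---|---|---|---|
| Power | 99% | 96% | 88% | 82% | 80% | 81% | 85% |

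Changing the ED share from 25% to 75% moves the control rate from 45% to 35% and leaves power at 80% to 81%. The baseline is therefore not the threat.

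**Does the effect in HIV-negative participants matter?** Let q be the HIV-positive share, b the PrEP-linkage rate under SOC and e the gain in PrEP linkage. People with HIV go from 40% to 55%, as in the plan. Then:

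- control rate = 0.40q + b(1 − q)
- intervention rate = 0.55q + (b + e)(1 − q)
- difference = 0.15q + e(1 − q)

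The documents give none of q, b or e, so the values below are assumptions. With b = 20% and 173 analysed per arm:

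| PrEP gain e | q = 10% | q = 25% | q = 50% |
|---|---|---|---|
| 0 points | 22.0% v 23.5%: 6% | 25.0% v 28.75%: 12% | 30.0% v 37.5%: 31% |
| +5 points | 22.0% v 28.0%: 25% | 25.0% v 32.5%: 34% | 30.0% v 40.0%: 50% |
| +10 points | 22.0% v 32.5%: 59% | 25.0% v 36.25%: 62% | 30.0% v 42.5%: 68% |
| +15 points | 22.0% v 37.0%: 87% | 25.0% v 40.0%: 85% | 30.0% v 45.0%: 83% |

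The 6% counts rejection in either direction; rejection in the expected direction alone is 5%. Elsewhere in the table the second tail changes nothing at this rounding.

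**Other assumed values.** Over q from 6% to 50% and b from 10% to 40%, power is at most 34% with no PrEP gain, about 18% to 53% with +5 points, 49% to 73% with +10, and 80% to 95% with +15. For example, with q = 50%, b = 40% and no PrEP gain, the contrast is 40% v 47.5%, power is 29%, and 80% power would need 686 per arm.

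**The case against.** The plan's calculation is right on its own terms. The 50% carries no HIV status, and the primary objective in section 2 covers linkage to care or prevention, so LTC in section 8.c may be shorthand for the composite. Hypothesis B in section 1 expects POC RNA testing to improve linkage to prevention services as well as treatment. No document figure shows a weaker effect on PrEP, and every low power above depends on values the documents do not supply. The enrolled group could also be richer in HIV than an ED population: eligibility names people with HIV who lack documented suppression, and one site cares for more than 3,000 people with HIV.

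Much of this stands, and it rules out several stronger readings:

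- A reader might infer that both input rates come from HIV-positive patients. Only the 30% is so described.
- A reader might infer that the figures show HIV status to be prognostic. They do not; the only contrast is ED against STD clinic.
- A reader might infer that 80% power needs a full 15-point gain in both groups. It does not. With a 10% PrEP base, 10% HIV-positive and a 12-point PrEP gain, the contrast is 13.0% v 25.3% and power is 83%.
- The ballpark label, and the recruitment sources left out of the 50/50 mix (the HIV specialty practice, community physicians, the public), do not in themselves lower power.

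The objection does not supply the missing inputs. A shared label does not provide a PrEP rate, and a hypothesis that prevention linkage improves does not say by how much.

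**Conclusion.** The point holds as a gap in justification. The 80% is correct for a composite that rises from 40% to 55%, but the documents give no ground for expecting that rise in a group that includes HIV-negative people. To conclude that the trial is underpowered would go too far, because the documents do not fix the HIV mix, the PrEP base or the PrEP effect.

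The size depends on the effect in HIV-negative participants. Under the illustrative assumptions (people with HIV 40% to 55%, PrEP base 20%, 10% to 50% HIV-positive, 173 analysed per arm), power runs from 6% to 31% with no PrEP gain, 59% to 68% with a 10-point gain, and 83% to 87% with a 15-point gain. The plan should show that dependence before 80% is quoted beside a result.

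**What to change.** 1. **Power statement (8.c).** Say that 80% power is conditional on the PrEP-or-ART composite rising from 40% to 55% in the HIV-status mix actually enrolled. State the assumed HIV-positive share and separate control rates and effects for ART and PrEP, derive the composite from them, and give power as a range.

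2. **Primary analysis (8.c).** The order of steps suggests that covariates follow from the bivariate results. Replace this with one pre-specified comparison of arms: a risk difference with 95% CI, adjusted for or stratified by site type and Day-0 HIV status. Define HIV status identically in both arms, from known status or the SOC algorithm on the Day-0 sample. Section 5 already runs that algorithm on all enrolment blood. The POC viral load must not enter the definition: only one arm has it by randomisation, and it could detect infections that the SOC algorithm misses.

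3. **Components.** Report PrEP linkage among HIV-negative participants by arm, beside ART start among HIV-positive participants, which is already planned.

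The cost is a change of text, slightly more analysis and a less favourable stated power. No extra participants are needed.
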